Appendix 3F: Insurance

LEO Pharma has taken out relevant insurances covering the subjects in the present clinical trial in accordance with applicable laws and regulations.

Appendix 3G: Financial disclosure

Investigators will provide LEO Pharma with sufficient, accurate financial information as requested to allow LEO Pharma to submit complete and accurate financial certification or disclosure statements to the appropriate regulatory authorities. Investigators are responsible for providing information on financial interests during the course of the clinical trial and for 1 year after completion of the clinical trial, or for a longer period of time if required by local legislation.

Appendix 3H: Trial and trial site closure

Premature termination of trial or trial site

LEO Pharma, the investigator, the IRB/IECs or competent authorities may decide to stop the clinical trial, part of the trial or a trial site at any time, but agreement on procedures to be followed must be obtained.

If a clinical trial is suspended or prematurely terminated, the investigator must inform the subjects promptly and ensure appropriate therapy and follow-up. As specified by applicable regulatory requirements, the investigator or LEO Pharma must promptly inform IRB/IECs and provide a detailed written explanation. Relevant competent authorities must be informed.

The trial must be terminated if the perception of the benefit/risk ratio (judged from clinical signs and symptoms, (S)AEs and/or remarkable safety laboratory changes) becomes unfavourable for the continuation of the trial.

Reasons for the early closure of a trial site by LEO Pharma or investigator may include but are not limited to:

- Failure of the investigator to comply with the protocol, the requirements of the IRB/IEC or local health authorities, LEO Pharma procedures, or GCP guidelines.
- Inadequate recruitment of subjects by the investigator.

Completion of trial

Investigators will be informed when subject recruitment is to cease. Screening activities will be stopped at a trial site when the total requested number of subjects for the clinical trial has been obtained, irrespective of the specific site's planned inclusion number.

Trial sites will be closed upon trial completion. LEO Pharma will undertake arrangements for the collection and disposal of any unused trial material that the investigator is not required to keep in his/her files. A trial site is considered closed when all required documents and trial supplies have been collected and a trial site closure visit has been performed.

When the randomisation code has been broken, the investigators will receive information about the treatment allocation for the subjects randomised at their respective sites and will be asked to record this in the subject's medical record.

Appendix 3I: Responsibilities

The signatory investigator is responsible for the approval of the clinical trial protocol and the CTR on behalf of all clinical trial investigators and as agreed to in a signatory investigator agreement.

Each participating investigator is responsible for all aspects of the clinical trial conduct at his/her trial site as agreed to in a clinical trial agreement.

Appendix 4: Hanifin and Rajka (1980) diagnostic criteria for AD (21)

Major Features: must have 3 or more of the following:

- Pruritus.
- Typical morphology and distribution:
 - Flexural lichenification or linearity in adults.
 - Facial and extensor involvement in infants and children.
- Chronic or chronically-relapsing dermatitis.
- Personal or family history of atopy (asthma, allergic rhinitis, atopic dermatitis).

Minor Features: should have 3 or more of the following:

- Xerosis.
- Ichthyosis, palmar hyperlinearity, or keratosis pilaris.
- Immediate (type 1) skin-test reactivity.
- Raised serum IgE.
- Early age of onset.
- Tendency toward cutaneous infections (especially *S. aureus* and *herpes simplex*) or impaired cell-mediated immunity.
- Tendency toward non-specific hand or foot dermatitis.
- Nipple eczema.
- Cheilitis.
- Recurrent conjunctivitis.
- Dennie-Morgan infraorbital fold.
- Keratoconus.
- Anterior subcapsular cataracts.
- Orbital darkening.
- Facial pallor or facial erythema.
- Pityriasis alba.
- Anterior neck folds.
- Itch when sweating.
- Intolerance to wool and lipid solvents.
- Perifollicular accentuation.
- Food intolerance.
- Course influenced by environmental or emotional factors.
- White dermographism or delayed blanch.

Appendix 5: Guidance for anaphylaxis diagnosis (24)

The National Institute of Allergy and Infectious Diseases (NIAID) and Food Allergy and Anaphylaxis Network Guidance for Anaphylaxis Diagnosis (FAAN) define anaphylaxis as a serious allergic reaction that is rapid in onset and may cause death. They recognise 3 categories of anaphylaxis, with criteria designated to capture from 80% of cases (category 1) to >95% of all cases of anaphylaxis (for all 3 categories).

Clinical criteria for diagnosing anaphylaxis

Anaphylaxis is highly likely when any one of the following 3 criteria are fulfilled:

- 1) Acute onset of an illness (minutes to several hours) with involvement of the skin, mucosal tissue, or both (e.g. generalized hives, pruritus or flushing, swollen lips-tongue-uvula).

AND AT LEAST ONE OF THE FOLLOWING:

- Respiratory compromise (e.g. dyspnea, wheeze-bronchospasm, stridor, reduced peak expiratory flow [PEF], hypoxemia).
- Reduced blood pressure (BP) or associated symptoms of end-organ dysfunction (e.g. hypotonia [collapse], syncope, incontinence).

- 2) Two or more of the following that occur rapidly after exposure to a likely allergen for that patient (minutes to several hours):

- Involvement of the skin-mucosal tissue (e.g. generalized hives, itch-flush, swollen lips-tongue-uvula).
- Respiratory compromise (e.g. dyspnea, wheeze-bronchospasm, stridor, reduced PEF, hypoxemia).
- Reduced BP or associated symptoms (e.g. hypotonia [collapse], syncope, incontinence).
- Persistent gastrointestinal symptoms (e.g. crampy abdominal pain, vomiting).

- 3) Reduced BP after exposure to known allergen for that patient (minutes to several hours):

- Infants and children: low systolic BP (age specific) or greater than 30% decrease in systolic BP.
- Adults: systolic BP of less than 90 mm Hg or greater than 30% decrease from that person's baseline.

Appendix 6: TCS classification list

English translation of the Japanese TCS classification list, which is included in the Guideline for Therapy for AD from 2018:

Group I Strongest	0.05%	Clobetasol propionate
	0.05%	Diflorasone diacetate
Group II Very Strong	0.1%	Mometasone fuorate
	0.05%	Betamethasone butyrate propionate
	0.05%	Fluocinonide
	0.064%	Betamethasone dipropionate
	0.05%	Difluprednate
	0.1%	Amcinonide
	0.1%	Diflucortolone valerate
	0.1%	Hydrocortisone butyrate propionate
	0.3%	Deprodone propionate
Group III Strong	0.1%	Dexamethasone propionate
	0.12%	Dexamethasone valerate
	0.12%	Betamethasone valerate
	0.025%	Fluocinolone acetonide
	0.3%	Prednisolone valerate acetate
Group IV Medium	0.1%	Triamcinolone acetonide
	0.1%	Alclometasone dipropionate
	0.05%	Clobetasone butyrate
	0.1%	Hydrocortisone butyrate
	0.1%	Dexamethasone
Group V Weak	0.5%	Prednisolone

Appendix 7: Short version of eligibility criteria

A short form (maximum 200 characters) version of each eligibility criteria for the trial is provided below.

No.	Inclusion criteria
1	Signed and dated informed consent has been obtained prior to any protocol-related procedures
2	Japanese subject aged 18 years and above
3	Diagnosis of AD as defined by the Hanifin and Rajka (1980) criteria for AD
4	History of AD for 1 year or more
5	Subjects with a recent history within 1 year before screening of inadequate response to treatment with topical medication or subjects for whom topical treatments are otherwise medically inadvisable
6	AD involvement of 10% (or more) body surface area at screening and at baseline according to component A of SCORAD
7	EASI score of 12 or more at screening and 16 or more at baseline
8	IGA score of 3 or more at screening and at baseline
9	Worst Daily Pruritus NRS average score of 4 or more during the week prior to baseline
10	Subjects must have applied a stable dose of emollient twice daily (or more, as needed) for at least 14 days before randomisation
11	Women of child bearing potential must use a highly effective form of birth control, confirmed by the investigator, throughout the trial and at least for 16 weeks after last administration of IMP

Abbreviation: AD, atopic dermatitis; EASI, Eczema Area and Severity Score; IGA, Investigator's Global Assessment; IMP, investigational medicinal product; NRS, numeric rating scale; SCORAD, Scoring Atopic Dermatitis.

No.	Exclusion criteria
1	Subjects for whom TCS are medically inadvisable in the opinion of the investigator
2	Concurrent enrolment in another interventional clinical trial
3	Previous randomisation in a tralokinumab clinical trial
4	Active dermatologic conditions that may confound the diagnosis of AD or would interfere with assessment of treatment, such as scabies, cutaneous lymphoma, or psoriasis
5	Known active allergic or irritant contact dermatitis that is likely to interfere with the assessment of severity of AD
6	Use of tanning beds or phototherapy (NBUVB, UVB, UVA1, PUVA) within 6 weeks prior to randomisation
7	Treatment with systemic immunosuppressive/immunomodulating drugs, systemic corticosteroids, or bleach baths within 4 weeks prior to randomisation
8	Treatment with TCS, TCI, topical PDE-4 inhibitors, or topical JAK inhibitors within 2 weeks prior to randomisation
9	Receipt of live attenuated vaccines within 30 days prior to randomisation and during the trial including the safety follow-up period
10	Receipt of any marketed or investigational biological agent (e.g. cell-depleting agents or dupilumab) within 6 months prior to randomisation or until cell counts return to normal, whichever is longer

11	Receipt of any investigational non-biologic agent within 5 half-lives prior to randomisation
12	Receipt of blood products within 4 weeks prior to screening
13	Major surgery within 8 weeks prior to screening or planned in-patient surgery or hospitalisation during the trial period
14	Known or suspected allergy or reaction to any component of the IMP or AxMP formulation
15	History of any active skin infection within 1 week prior to randomisation
16	History of a clinically significant infection (systemic infection or serious skin infection requiring parenteral treatment) within 4 weeks prior to randomisation
17	A helminth parasitic infection within 6 months prior to the date informed consent is obtained that has not been treated with, or has failed to respond to, standard of care therapy
18	History of anaphylaxis following any biological therapy
19	History of immune complex disease
20	History of cancer
21	Tuberculosis requiring treatment within the 12 months prior to screening. Evaluation will be according to local guidelines as per local standard of care
22	History of any known primary immunodeficiency disorder including a positive HIV test at screening, or the subject taking antiretroviral medications
23	History of chronic alcohol or drug abuse within 12 months prior to screening, or any condition associated with poor compliance as judged by the investigator
24	History of attempted suicide or at significant risk of suicide (either in the opinion of the investigator or on the C-SSRS)
25	Any disorder, which is not stable and in the investigator's opinion could affect the safety of the subject, influence the findings of the trial, or impede the subject's ability to complete the trial
26	Any abnormal finding, which in the investigator's opinion may put the subject at risk, influence the results of the trial, or influence the subject's ability to complete the trial
27	ALT or AST level 2.0 times the upper limit of normal or more at screening
28	Positive HBsAg, HBsAb, HBcAb, or anti-HCV serology at screening. Subjects with positive HBsAb may be randomised provided they have negative HBsAg, HBcAb, and HCV serology
29	Subjects who are not willing to abstain from donating blood and/or plasma from the time of informed consent and for 16 weeks (5 half-lives) after last dose of IMP
30	Subjects who are legally institutionalised
31	Pregnant, breastfeeding, or lactating women
32	Employees of the trial site or any other individuals directly involved with the planning or conduct of the trial, or immediate family members of such individuals

Abbreviations: AD, atopic dermatitis; ALT, alanine aminotransferase; anti-HCV, hepatitis C virus antibody; AST, aspartate aminotransferase; AxMP, auxiliary medicinal product; C-SSRS, Columbia-Suicide Severity Rating Scale; HBcAb, hepatitis B core antibody; HBsAb, hepatitis B surface antibody; HBsAg, hepatitis B surface antigen; HIV, human immunodeficiency virus; IMP, investigational medicinal product; JAK, Janus kinase; NBUVB, narrow band ultraviolet B; PDE-4, phosphodiesterase-4; PUVA, psoralen + ultraviolet A; TCI, topical calcineurin inhibitors; TCS, topical corticosteroids; UVA1, ultraviolet A1; UVB, ultraviolet B.

FAS	full analysis set
ICH	International Council for Harmonisation of Technical Requirements for Pharmaceuticals for Human Use
IGA	Investigator's Global Assessment
IGA 0/1	IGA response of 0 (clear) or 1 (almost clear)
IMP	investigational medicinal product
MAR	missing at random
MedDRA	Medical Dictionary for Regulatory Activities
MI	multiple imputation
NRS	numeric rating scale
POEM	Patient Oriented Eczema Measure
PYE	patient years of exposure
Q2W	every 2 weeks
QC	quality control
SAP	statistical analysis plan
SCORAD	Scoring Atopic Dermatitis
SOC	(MedDRA) system organ class
SOP	standard operating procedure
TCS	topical corticosteroid(s)

Trial ID: LP0162-1343	Date: 15-Jun-2021	Version: 1.0 Page 7 of 22
-----------------------	-------------------	------------------------------

4 Introduction

The statistical analysis will be performed as outlined in the clinical trial protocol.

This statistical analysis plan is prepared before the unblinding of the trial and supplements the clinical trial protocol, which otherwise describes the originally planned statistical analyses of all endpoints in an intended exhaustive manner. The statistical analysis plan contains a more technical and detailed elaboration of some points related to the implementation of the statistical analysis already described in the clinical trial protocol.

In addition, the statistical analysis plan includes supplementary statistical analyses and aspects that are introduced after the protocol.

New analyses:

The analyses of the other endpoints, reduction from baseline to Week 16 of DLQI \geq 4 among subjects with baseline DLQI \geq 4 and reduction from baseline to Week 16 of POEM score \geq 4 points in subjects with baseline POEM score \geq 4, will be analysed by applying the composite estimand. In addition, the same endpoints will be evaluated at each scheduled visit/assessment up to Week 12.

A repeated measurements analysis of the change from baseline in EASI score from baseline to Week 16 has been added.

Trial completers will be defined as stated in the protocol. Reason for not completing the trial will be assessed using the alternatives listed for not attending the safety follow-up visit except for the alternatives ‘transferred to 1337’ and ‘safety follow-up information collected at nominal Week 16 visit’.

A descriptive presentation of IGA 0/1 and EASI75 at week 16 by baseline IGA have been added.

5 Trial analysis sets

The trial analysis sets are defined in the protocol and the following modifications to the analysis sets are introduced.

All subjects who are randomised to treatment and exposed to IMP will be included in the full analysis set (FAS) and will be analysed for efficacy up to Week 16. Exclusions from the FAS can be considered in special cases as described in the ICH E9 guideline, Section 5.2.1. If it is

Trial ID: LP0162-1343	Date: 15-Jun-2021	Version: 1.0 Page 8 of 22
-----------------------	-------------------	------------------------------

decided to exclude a randomised and exposed subject from the FAS, a justification addressing ICH E9 will be given.

As stated in the protocol, a safety analysis set will be defined as all randomised subjects who receive IMP.

In addition to the analysis sets defined in the protocol, a safety follow-up analysis set will be used as the basis for evaluation of adverse events during the safety follow-up period. It comprises all subjects for whom date of last contact is after the date of exposure end, where exposure end is defined as the Week 16 visit for subjects completing the treatment period, and otherwise the date of permanent discontinuation of IMP (tralokinumab/placebo) for subjects not completing the treatment period. See also Section [6.8.2](#) for further details.

For analysis of efficacy, subjects will be analysed ‘as randomised’.

For analysis of safety, subjects will be analysed ‘as treated’ according to the following rule: subjects who received at least one dose of tralokinumab will be analysed in the tralokinumab treatment group. Although this may dilute the AE rate in the tralokinumab treatment group slightly by including in the denominator subjects who only received one dose of active treatment, it will ensure that no significant drug reactions to tralokinumab will erroneously be assigned to placebo.

The decisions regarding inclusion/exclusion of subjects from the trial analysis sets will be documented in the analysis set definition document before breaking the randomisation code.

6 Statistical Analysis

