lesional skin, emollients should only be applied at a time when TCS is not applied; on TCS-untreated areas, the emollients may be applied at all times. The emollient treatment is further described in Section 9.4.

Eligibility will be assessed both at the (first) screening visit and prior to randomisation at baseline (Week 0; Visit 3) as described in Section 8.

Treatment period (Week 0 to Week 16)

Following the screening period, eligible subjects will be randomly assigned to one of the following treatment groups:

- Tralokinumab 600 mg (4 mL) at baseline, then 300 mg (2 mL) Q2W + TCS.
- Placebo (4 mL) at baseline, then placebo (2 mL) Q2W + TCS.

The IMPs, tralokinumab and placebo, are described in Section 9.1.1 and the treatment assignment is described in Section 9.3. The IMP will be administered by subcutaneous (SC) injections every second week throughout the treatment period as described in Section 9.2. The last dose of IMP will be administered at Week 14.

Subjects in both treatment groups will also be supplied with an AxMP, i.e. a TCS cream (mometasone furoate) as described in Section 9.1.2. The subjects will apply a thin film of the supplied TCS once daily on areas with active lesions as needed and as described in Section 9.2.2. Lower potency TCS or TCI may be prescribed if needed on body areas where the supplied TCS is not advisable or on areas where continued treatment with TCS is considered unsafe. Topical therapy should be discontinued when control is achieved; discontinuation should preferably be gradual. The safety and appropriateness of continued or repeated courses of TCS therapy will be monitored and supervised by the site staff.

Subjects who during the treatment period or safety follow-up experience intolerable AD symptoms can be treated with rescue treatment according to investigators discretion as described in Section 9.5.

Subjects, who complete the 16-week treatment period, may be invited to enter a long-term extension trial conducted under a separate protocol (ECZTEND).

Safety follow-up period (Week 16 to Week 20)

After the treatment period, all subjects who do not enter the long-term extension trial will complete an off-treatment follow-up period for assessment of safety, PK, and ADA.

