All subjects completing the treatment period, except for those who enter the long-term extension trial, will have safety follow-up assessments 6 weeks after last IMP administration. Subjects who permanently discontinue IMP or withdraw from the trial will be followed up as described in Section 10.

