13.2 Collection of adverse event reports

AE data must be collected from time of first trial-related activity after the subject has signed the informed consent form until completion of the trial (defined as the safety follow-up visit 6 weeks after last IMP injection) [Sections [7.3](#) and [10.3](#)]. For subjects entering the long-term extension trial (ECZTEND), any (S)AE with onset before the final visit in LP0162-1343 should be reported in LP0162-1343. If ongoing, the (S)AE will also be recorded as medical history in ECZTEND.

AEs must be assessed by medically qualified personnel.

At all visits, the subject will be asked a non-leading question by the investigator about AEs, for example: “How have you felt since I saw you last?” No specific symptoms should be asked for. It is important that the investigator also observes the subject for any changes not reported by the subject and records these changes.

Refer to Sections [11.4.1](#) to [11.4.4](#) for principles for data entry in the eCRF.

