13.7 Follow-up for final outcome of adverse events

During the trial, the investigator should follow up for final outcome on all AEs (including SAEs). Once a subject leaves the clinical trial, the investigator should follow up on the outcome of all non-serious AEs classified as of possibly or probably related to the IMP for 2 weeks or until the final outcome is determined, whichever comes first. SAEs must be followed up until a final outcome has been established, that is, the follow-up may continue beyond the end of the clinical trial. For SAEs which have stabilised and from which the subject cannot be expected to recover during the trial or the safety follow-up periods, for example chronic or stabilised conditions, the final outcome at the investigator's discretion should be reported as 'recovering/resolving' or 'not recovered/not resolved'. In addition, a statement detailing why the subject cannot be expected to recover during the trial e.g. that the SAE has stabilised or is chronic should be added to the narrative description of the SAE on the SAE form.

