6.8.2 Definition of trial periods and date of permanent discontinuation of IMP

Date of permanent discontinuation of IMP

Defined for subjects who have a reason for permanent discontinuation of IMP recorded.

Defined as the latest of date of early termination visit (if existing) or date of onset of latest AE leading to withdrawal of trial product, otherwise date of the last visit, excluding safety follow-up and nominal Week 16 visits.

Exposure start

Date and time of first dose.

Exposure end

Date of Week 16 visit (if existing) at time 23:59:00, otherwise date of permanent discontinuation of IMP (if existing) at time 23:59:00, otherwise date of last IMP administration at time 23:59:00.

Trial ID: LP0162-1343	Date: 15-Jun-2021	Version: 1.0 Page 19 of 22
-----------------------	-------------------	-------------------------------

Date of last contact

Date of very last contact found by examining all time and date information in eCRF, laboratory, ECG, and PRO.

Trial periods

The time from exposure start to exposure end will be assigned to the treatment period and remaining time after exposure end will be assigned to the safety follow-up period as shown in [Table 4](#) (ADaM variable APHASE). The ADaM variable APERIODC will indicate the latest treatment at any given time point, thus not including a follow-up period ([Table 5](#)).

Table 4: Start and end time of trial periods (ADaM variable APHASE)

APHASE	Start of period	End of period (only if start date exists)
Treatment period	Exposure start	Exposure end
Safety follow-up period ¹	First day after exposure end	Date of last contact at time 23:59:00

1) Only applicable if date of last contact is not equal to date of exposure end.

Table 5: Start and end time of trial periods (ADaM variable APERIODC)

APERIODC	Start of period	End of period (only if start date exists)
Treatment period	Exposure start	Date of last contact at time 23:59:00

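### The safety follow-up analysis set can count ECZTEND transfers who left at Week 16 but have a later recorded date, although new AEs are no longer collected for them in this trial

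*SAP*

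**What the plan says.** SAP Section 5 adds a safety follow-up analysis set as the basis for evaluating AEs in the follow-up period. Its membership rule is: "It comprises all subjects for whom date of last contact is after the date of exposure end". SAP Section 6.8.2 supplies the two dates.

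- Exposure end, for a subject with a Week 16 visit: "Date of Week 16 visit (if existing) at time 23:59:00".
- Last contact: "Date of very last contact found by examining all time and date information in eCRF, laboratory, ECG, and PRO".

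Table 4 in the same section gives each subject a follow-up period running to last contact, with the footnote "Only applicable if date of last contact is not equal to date of exposure end".

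The protocol describes who is actually followed.

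- Section 7.1: "all subjects who do not enter the long-term extension trial will complete an off-treatment follow-up period". It also says that treatment completers, "except for those who enter the long-term extension trial, will have safety follow-up assessments 6 weeks after last IMP administration".
- Section 13.2, for subjects entering ECZTEND: "any (S)AE with onset before the final visit in LP0162-1343 should be reported in LP0162-1343".
- Section 13.7: once a subject has left, non-serious AEs possibly or probably related to IMP are followed for up to 2 weeks. SAEs are followed to a final outcome, and "the follow-up may continue beyond the end of the clinical trial".

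**The concern.** The follow-up AE summary is meant to describe the off-treatment weeks, so its denominator should hold subjects in whom an off-treatment AE could have been recorded. The SAP's rule tests something else: whether any date later than Week 16 exists. For a transfer whose last visit here was Week 16, such a date can arise from outcome follow-up of an old event, while the reporting window for new events has closed. That subject adds one to the denominator and is not due to add anything to the numerator. No passage in either document removes such a subject.

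At stake is the reading of a safety table. Percentages of subjects with follow-up AEs would be understated. Subjects admitted through outcome follow-up are also selected for having an event still open at Week 16. If that share or the transfer fraction differed between arms, the understatement would differ too, though nothing in the documents shows that it would.

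**Working it through.** The plan states no size, transfer fraction or AE rate for this set, so there is no figure to reproduce. The check has two parts.

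**1. Membership logic for a treatment completer who transfers, with Week 16 as last visit**

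| Latest date on file | Last contact after exposure end? | In the set? | New AEs collected here after Week 16? |
|---|---|---|---|
| Week 16 visit | No | No (strict rule in SAP 5; Table 4 footnote) | No |
| Later date, e.g. AE stop date from Protocol 13.7 follow-up | Yes | Yes | No (Protocol 13.2) |

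Protocol Appendix 2 requires a stop date when an event is recorded as resolved, so the second row can occur. SAP 6.8.3 also sets a partly missing medication end date to the last day of the month or year. The SAP does not say whether such imputed dates count towards last contact.

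**2. Size, as an illustration**

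Input from the documents: about 100 randomised 1:1, so about 50 per arm. The follow-up period is 4 weeks (28 days).

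Assumed, because the documents do not give them: transfer fraction 50%, 70% or 90%; q = share of transfers with a date after Week 16; true follow-up AE percentage 20%. For simplicity every non-transfer is taken as followed up.

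Let T = transfers and F = 50 − T.

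Dilution factor for a percentage = F / (F + q × T)

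| Transfer fraction | F | T | q = 0 | q = 10% | q = 25% |
|---|---|---|---|---|---|
| 50% | 25 | 25 | 1.00 | 25/27.5 = 0.91 | 25/31.25 = 0.80 |
| 70% | 15 | 35 | 1.00 | 15/18.5 = 0.81 | 15/23.75 = 0.63 |
| 90% | 5 | 45 | 1.00 | 5/9.5 = 0.53 | 5/16.25 = 0.31 |

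At 70% transfer, a true 20% would be shown as 16.2% (q = 10%) or 12.6% (q = 25%).

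For a rate per person-time, a stray date adds only the days up to that date. Assume it falls 7 days after Week 16:

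Factor = 28F / (28F + 7qT)

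At 70% transfer, 28 × 15 = 420 days.

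- q = 10%: 420 / (420 + 24.5) = 0.95
- q = 25%: 420 / (420 + 61.25) = 0.87

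If the set holds only subjects under AE collection after exposure end, the factor is 1.00 in every cell.

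**The case against.** The strongest reply is that the rule already removes most of the problem. A transfer whose last recorded date is the Week 16 visit is not in the set, so a reader who infers that transfers as a group inflate the denominator goes further than the documents allow. This stands in full, and it is why the size depends on q.

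The other arguments:

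- **The entry route is narrow.** Protocol 13.7 covers only IMP-related non-serious AEs, for at most 2 weeks, and SAEs. It does not cover unrelated non-serious AEs or open medications, and Protocol 9.6 records a medication still in use as ongoing. For transfers, ongoing events are also carried into ECZTEND as medical history, so how often a later stop date reaches this trial's eCRF is unknown. This stands: q could be small.
- **New events are not always impossible.** The cut-off in Protocol 13.2 is the final visit in this trial, and the end of trial form (Protocol 11.8) records which visit that was. An AE with onset before a later final visit would still be reported here. This stands, and limits the point to transfers whose last visit was Week 16.
- **Decisions on the analysis sets are documented before the code is broken.** True, but neither document gives a rule for transfers, so this is an opportunity to correct the set and not a correction.
- **The summary is only descriptive.** True. There is no formal testing, and all AEs are listed.

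None of this changes the fact that the written rule admits subjects who are no longer under AE collection.

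**Conclusion.** The point holds as a minor defect in a set definition. As written, the rule puts into the follow-up denominator any ECZTEND transfer with Week 16 as last visit and a later recorded date. The effect on AE percentages is nil at q = 0. At an assumed 70% transfer it is a factor of about 0.81 at q = 10% and 0.63 at q = 25%. It is smaller if rates per person-time are shown, and the SAP does not say which measure the follow-up AE summaries will use. The overall AE summary in Protocol 14.3.12.1 is in numbers and percentages of subjects.

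The transfer fraction, q and the 20% AE percentage are assumptions. A reader might infer that follow-up AE rates will certainly be biased low, or biased differently by arm. The documents support neither, because both depend on quantities they do not report. Efficacy and the secondary endpoint on treatment-emergent AEs from baseline to Week 16 are unaffected.

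**What to change.** In SAP Sections 5 and 6.8.2, make one of two changes:

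1. Exclude from the safety follow-up analysis set subjects whose end of trial form records transfer to ECZTEND with Week 16 as the last visit attended.
2. For this set only, define date of last contact by visits or contacts at which AEs were collected, and not by AE or medication stop dates.

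The exclusion should not extend to all transfers: an AE with onset after Week 16 but before a later final visit would then lose its period and its denominator.

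The cost is one or two sentences. Under the first option the transfer flag and the last visit attended are already on the end of trial form (Protocol 11.8). No other analysis changes if a new last-contact date is confined to this set.
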